#### **4.2.5 Best Overall Response Rate**

Primary BORR definition is defined as the number of subjects in the arm with a BOR of CR or PR, divided by the total number of randomized subjects in the arm.

Per protocol BORR definition is defined as the number of response evaluable subjects in the arm with a BOR of CR or PR, divided by the total number of response evaluable subjects in the arm.

#### **4.2.6 Duration of Response**

Primary duration of response (DoR) definition for the randomized subjects whose BOR is CR or PR is defined as the time between the date of response of CR or PR (whichever occurs first) and the first date of progressive disease (PD) or the date of death (whichever occurs first).

Per protocol DoR definition for the response evaluable subjects whose BOR is CR or PR is defined as the time between the date of response of CR or PR (whichever occurs first) and the first date of progressive disease (PD) or the date of death (whichever occurs first).

For both definitions, for subjects who underwent tumor resection following response but prior to disease progression, DoR will be censored on the date of the last evaluable TA prior to resection. For subjects who remain alive and have not progressed following response, DoR will be censored on the date of last evaluable TA prior to subsequent therapy.

#### **4.2.7 Duration of Stable Disease**

Primary duration of stable disease (DoSD) definition for the randomized subjects whose BOR is SD is defined as the time between the randomization date and the first date of PD or the date of death (whichever occurs first).

Per protocol DoSD definition for the response evaluable subjects whose BOR is SD is defined as the time between the randomization date and the first date of PD or the date of death (whichever occurs first).

For both definitions, for subjects who underwent tumor resection following SD but prior to disease progression, DoSD will be censored on the date of the last evaluable TA prior to resection. For subjects who remain alive and have not progressed following SD, DoSD will be censored on the date of last evaluable TA prior to subsequent therapy.

## 5 SAMPLE SIZE AND POWER

Approximately 180 Chinese subjects will be randomized to ipilimumab and DTIC at a 2:1 ratio and followed at least 2 years after randomization to ensure 80% power through simulation using a chi-squared test with a Type I error rate of 0.20 to reject the null hypothesis of no difference in 2-year survival rate between treatment groups, assuming a HR [ipilimumab vs DTIC] of 0.67. Under an exponential distribution, this hazard ratio (HR) would correspond to an 12 month median OS for the ipilimumab arm with an 8 month median OS in the DTIC arm^8(or equivalently 25% and 12.5% in the ipilimumab and DTIC arm). The accrual duration is approximately 18 months, assuming a monthly rate of 10 subjects per month. The primary analysis will be performed about 42 months after the first subject is randomized.

## 6 STUDY PERIODS, TREATMENT REGIMENS AND POPULATIONS FOR ANALYSES

## 6.1 Study Periods

- Baseline period:
  - Baseline evaluations or events will be defined as evaluations or events that occur before the date and time of the first dose of study treatment. Evaluations on the same date and time of the first dose of study treatment will be considered as baseline evaluations.
  - In cases where the time (onset time of event or evaluation time and dosing time) is missing or not collected, the following definitions will apply:
    - ◆ Pre-treatment AEs will be defined as AEs with an onset date prior to but not including the day of the first dose of study treatment.
    - ◆ Baseline evaluations (laboratory tests, etc.) will be defined as evaluations with a date on or prior to the day of first dose of study treatment.

If there are multiple valid assessments, the assessment that is closest to day (and time if collected) of the first dose of study treatment will be used as the baseline in the analyses. If multiple assessments are collected on the same date (and time, if collected), the assessment with the latest database entry date (and time, if collected) will be considered as baseline, unless mentioned otherwise.

- Post baseline period:
  - On-treatment AEs will be defined as AEs with an onset date and time on or after the date and time of the first dose of study treatment (or with an onset date on or after the day of first dose of study treatment if time is not collected or is missing). For subjects who are off study treatment, AEs will be included if event occurred within a safety window of 90 days after the last dose of study treatment. No ‘subtracting rule’ will be applied when an AE occurs both pre-treatment and posttreatment with the same preferred term and grade.
  - On-treatment evaluations (laboratory tests, etc.) will be defined as evaluations taken after the day (and time, if collected and not missing) of first dose of study treatment. For subjects who are off study treatment, evaluations should be within a safety window of 90 days after the last dose of study treatment.

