## SYNOPSIS

### Clinical Protocol CA184248

**Protocol Title:** A Randomized, Open-Label, Two-arm, Comparative Study in Chinese Subjects with Chemotherapy Naïve Stage IV Melanoma Receiving Ipilimumab (3 mg/kg) vs. Dacarbazine.

**Investigational Product(s), Dose and Mode of Administration, Duration of Treatment with Investigational Product(s):** ipilimumab 3 mg/kg to be administered via intravenous infusion over 90 minutes at Weeks 1, 4, 7 and 10, for a total of four doses in Induction (and Re-Induction for those randomized to the ipilimumab arm who qualify) and DTIC 250 mg/m^2 - Day 1 - 5, to be administered via intravenous infusion at Weeks 1, 4, 7, 10, 13, 16, 19, and 22.

In this protocol amendment, investigational product is: Ipilimumab 5 mg/mL solution.

**Study Phase:** II

**Research Hypothesis (for the Induction phase):** Among chemotherapy naive Chinese subjects with Stage IV melanoma, the 2-year OS (OS) rate in Chinese subjects who have been randomized to ipilimumab 3 mg/kg will be superior to that in Chinese subjects who have been randomized to DTIC 250 mg/m^2 - Day 1 - 5. Database lock date was 03Jun2019.

No formal research hypothesis will be tested in the Re-Induction phase.

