### **7.6.1 Adverse Events**

#### **Adverse Events, Serious Adverse Events**

The following summary tables of AEs and SAEs will be restricted to events occurring in the on-study phase (see [Section 4.3.1.1](#)).

- On-study phase AEs (worst CTC grade [Any grade, 3-4, 5] of any event and of events by SOC)
- On-study phase AEs (worst CTC grade [1, 2, 3, 4, 5, unknown, any grade] of any event and of events by SOC)
- On-study non-serious AEs occurring in at least 5% of subjects (worst CTC grade [Any grade, 3-4, 5] of any event and of events by SOC)
- On-study phase SAEs (worst CTC grade [Any grade, 3-4, 5] of any event and of events by SOC)
- On-study phase SAEs (worst CTC grade [1, 2, 3, 4, 5, unknown, any grade] of any event and of events by SOC)
- On-study phase drug-related AEs (worst CTC grade [Any grade, 3-4, 5] of any event and of events by SOC)
- On-study phase drug-related AEs (worst CTC grade [1, 2, 3, 4, 5, unknown, any grade] of any event and of events by SOC)
- On-study phase drug-related SAEs (worst CTC grade [Any grade, 3-4, 5] of any event and of events by SOC)
- On-study phase drug-related SAEs (worst CTC grade [1, 2, 3, 4, 5, unknown, any grade] of any event and of events by SOC)

- On-study phase AEs leading to discontinuation of ipilimumab (worst CTC grade [Any grade, 3-4, 5] of any event and of events by SOC)
- On-study phase AEs leading to discontinuation of ipilimumab (worst CTC grade [1, 2, 3, 4, 5, unknown, any grade] of any event and of events by SOC)

Listings by subject will be produced for all AEs (including drug-related AEs and those leading to discontinuation of ipilimumab), all AEs leading to discontinuation of ipilimumab (including drug-related AEs), all SAEs (including drug-related SAEs).

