## **Multiple Events Analyses**

For the multiple event analyses, the following summary tables will be provided:

- A table showing the total number and rate (exposure-adjusted) of occurrences for all on-study AEs occurring in at least 5% of the subjects treated
- A table showing the total number and rate (exposure-adjusted) of occurrences for all on-study irAEs
- A table showing the number of subjects experiencing an on-study AE once or multiple times

No formal comparisons/statistical testing will be performed. A listing will be produced that displays the unique instances of all AEs, i.e. after duplicates have been eliminated and overlapping and contiguous occurrences of the same event have been collapsed.

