### ***7.6.3 Deaths***

Deaths will be analyzed based on all treated subjects.

- All deaths (with reason)
- Deaths within 30 days of last dose received
- Deaths within 90 days of last dose received

All deaths, together with the reason, will be listed by subject; deaths occurring within 30 days following the last day of study treatment, and within 90 days following the last day of study treatment will be indicated.

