## 8 CONVENTIONS

Unless otherwise noted, the following conventions should be understood to apply. Further conventions may be detailed in the Data Presentation Plan.

The duration between two dates will be calculated as [later date] – [earlier date] + 1 day. Study day will be calculated as

$$Day = \begin{cases} [\text{assessmentdate}] - [\text{first medicationdate}], & \text{if assessment before first medication,} \\ [\text{assessmentdate}] - [\text{first medicationdate}] + 1 \text{ day,} & \text{if assessment on or after first medication} \end{cases}$$

Assessment times will be calculated relative to the first date of study medication, i.e. Day 1.

Events will be considered as occurring within X days (e.g. deaths within 30 days, deaths and AEs within 90 days) of last dose of study medication if [event date] – [last dosing date] ≤ X.

The following factors will convert days to months or years: 1 month = 30.4375 days, 1 year = 365.25 days.

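### By-arm SAE and Grade 3-5 AE tables are crude proportions over windows that differ by regimen (154 vs 242 days for completers), with no time-adjusted counterpart in the readable SAP

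*SAP*

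**What the plan says.** **Window.** SAP 6.1 starts the AE period at first dose. For subjects off treatment, "AEs will be included if event occurred within a safety window of 90 days after the last dose of study treatment". SAP 8 gives the matching date rule: "Events will be considered as occurring within X days (e.g. deaths within 30 days, deaths and AEs within 90 days", measured from the last dosing date.

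**Schedules.** The Protocol synopsis gives ipilimumab "at Weeks 1, 4, 7 and 10, for a total of four doses in Induction" and DTIC "Day 1 - 5, to be administered via intravenous infusion at Weeks 1, 4, 7, 10, 13, 16, 19, and 22".

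**Tables.** By default, SAP 7.1 reports frequencies and proportions of subjects by treatment, and SAP 7.6 presents safety by arm in all treated subjects. A typical entry in 7.6.1 is "On-study phase SAEs (worst CTC grade [Any grade, 3-4, 5] of any event and of events by SOC". The AE and drug-related AE tables have the same form.

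**Time adjustment.** Under Multiple Events Analyses, SAP 7.6.1 plans a table of "the total number and rate (exposure-adjusted) of occurrences for all on-study AEs occurring in at least 5% of the subjects treated", and a second such table for all on-study irAEs. No exposure-adjusted table for SAEs or Grade 3-5 AEs appears in the readable text.

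**Text not available.** SAP 7.6.1 refers to Section 4.3.1.1 for the on-study phase. That section is in the contents list, but its text is not in the public document. This is not a fault of the plan, but it limits what can be concluded.

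**The concern.** A proportion of subjects with at least one event grows with time observed. If one arm is observed longer because its regimen is longer, its proportion can be higher at the same underlying risk. Here the comparator has the longer planned regimen, so among completers the artefact would make DTIC look worse.

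The plan recognises the issue for common AEs and irAEs by adding occurrence rates adjusted for exposure. SAEs and Grade 3-5 AEs are the tables that readers of a by-arm safety section look at first, and they have no such companion. A less common serious or severe event falls below the 5% threshold and, unless it is an irAE, would appear only as a crude proportion.

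**Working it through.** **Inputs**
- Ipilimumab Induction: last dose at Week 10 (Protocol synopsis).
- DTIC: five daily doses per cycle, last cycle at Week 22 (Protocol synopsis).
- Follow-up after last dose: 90 days (SAP 6.1), counted as event date minus last dosing date ≤ 90 (SAP 8).
- Week-to-day conversion: day = 7 × (week − 1) + 1.

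**Check of the conversion.** It reproduces the day labels printed in Protocol Table 5.1-1: Week 4 = 22, Week 7 = 43, Week 10 = 64, Week 12 = 78, Week 24 = 162. The documents state no total window length, so there is no further figure to reproduce.

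**Windows for completers**
- Ipilimumab: last dose Day 64; 64 + 90 = Day 154.
- DTIC: Week 22 starts on Day 7 × 21 + 1 = 148; fifth dose on Day 148 + 4 = 152; 152 + 90 = Day 242.
- Difference 242 − 154 = 88 days; ratio 242/154 = 1.57. (Counting from the first day of the Week 22 cycle gives 148 + 90 = 238.)

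**Windows when DTIC stops early**, against an ipilimumab completer. Last DTIC dose after c cycles is Day 21 × (c − 1) + 5.

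| DTIC cycles given | Last dose | Window end | Ratio to 154 |
|---|---|---|---|
| 3 (to Week 7) | Day 47 | Day 137 | 0.89 |
| 4 (to Week 10) | Day 68 | Day 158 | 1.03 |
| 6 (to Week 16) | Day 110 | Day 200 | 1.30 |
| 8 (to Week 22) | Day 152 | Day 242 | 1.57 |

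Early stopping will be common. Progression requires discontinuation (Protocol 3.5), and the first scheduled on-treatment Induction scan was at Week 12 (Protocol 5.4.2), after the Week 10 cycle and before the Week 13 cycle. Also, under the SAP's planning assumption of an 8-month median OS on DTIC (8 × 30.4375 = 243.5 days, exponential), the proportion alive at Day 152 is 0.5^(152/243.5) = 0.65. On that assumption about 65% is a ceiling on DTIC completers, before progression or toxicity is counted.

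**Effect on a crude proportion: completers only, equal constant hazard (assumed).** If p is the proportion by Day 154, the proportion by Day 242 is 1 − (1 − p)^(242/154).

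| By Day 154 | By Day 242 |
|---|---|
| 10% | 15.3% |
| 20% | 29.6% |
| 30% | 42.9% |

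**Effect on a person-time rate.** With p = 20%, the hazard is −ln(0.80)/154 = 0.00145 per day. From the longer window, −ln(1 − 0.296)/242 = 0.00145 per day. A rate with person-time over the counting window therefore removes the artefact under this assumption.

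**The case against.** Several points on the other side stand.

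- **Describing each regimen as given is coherent.** The extra DTIC time exists because DTIC is still being given, and both arms get the same 90-day tail. The readable objectives (SAP 3.1 and 3.2) include no safety comparison, and SAP 7.6 tests nothing between arms. The tables are by-arm descriptions, so no stated comparison is invalidated.
- **The gap is not fixed.** The ratio of 1.57 applies only where subjects in both arms complete. It is close to 1 when DTIC stops after Week 10 and reverses when it stops earlier. A reader might infer that DTIC proportions are inflated by about half; the documents do not support that, because they give no distribution of cycles received.
- **Part of the gap is already covered.** Common AEs of any grade or causality, and all irAEs (which are selected on drug relationship), are in the exposure-adjusted tables.

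Three stronger readings are tempting and should not be drawn.

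- *That mortality is distorted in the same way.* SAP 7.6.3 does list "Deaths within 90 days of last dose received" and a 30-day version, but also a table of all deaths with no window. SAP 7.5.1 and 7.5.2 analyse survival from randomization.
- *That re-induction lengthens the ipilimumab window in the AE tables.* SAP 6.1, read literally, does not limit last dose to Induction. However, the on-study definition is in the unavailable Section 4.3.1.1, and SAP 7.6.1 tabulates novel re-induction imARs separately. This is a point to clarify.
- *That the exposure-adjusted rates use a mismatched denominator.* None is given in the readable text, but it may be in the missing section.

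**Conclusion.** The point holds in a limited form. The by-arm SAE and Grade 3-5 AE tables are crude proportions over windows set by regimen length, and the readable SAP gives them no time-adjusted companion. For completers the windows are 154 and 242 days, ratio 1.57, the planned maximum from Induction. The actual average gap depends on cycles received, which the documents do not report, and it could be small or run the other way. The step from 20% to 29.6% is an illustration that needs full completion and an equal constant hazard in both arms; it is not an estimate for this trial.

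The primary two-year survival analysis and OS are unaffected. This is an inexpensive improvement to how safety is reported. It does not show that the planned safety tables are wrong.

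**What to change.** In SAP 7.6.1, under Multiple Events Analyses:

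1. Extend the exposure-adjusted table to SAEs, Grade 3-5 AEs and drug-related AEs. State the denominator: person-time from first dose to last dose + 90 days, or to death or data cut-off if earlier, which is the window in which events are counted. If Section 4.3.1.1 already defines exposure this way, a cross-reference is enough.
2. Optionally, add a supplementary cumulative incidence of SAEs and Grade 3-5 AEs through a common day from first dose, censored at last dose + 90 days. If Day 154 is used, add a footnote that a DTIC completer then has 154 − 152 = 2 days of post-dose follow-up, against 90 for an ipilimumab completer. Late DTIC events stay in the full tables.
3. If Section 4.3.1.1 does not already do so, show AEs with onset after the first Re-Induction dose separately in the by-arm AE and SAE tables, and divide person-time at the same point.

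The crude tables should stay. The cost is SAP wording and a few more outputs from dose and event dates already held. As the Protocol gives database lock as 3 June 2019, tables added after that date should be labelled supplementary.

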## 6.2 Treatment Regimens

The treatment group “**as randomized**” will be retrieved from the IVRS system

- Arm A: ipilimumab
- Arm B: DTIC

The treatment group “**as treated**” will be the same as the arm randomized by IVRS. However, if a subject received the incorrect drug for **the entire period** of treatment, the subject’s treatment group will be defined as the incorrect drug the subject actually received.

## 6.3 Populations for Analyses

The statistical analyses in this study will be defined with respect to the following data sets.

**All Enrolled Subjects:** All subjects who signed an informed consent form and were registered into the IVRS. Subject disposition will be based on all enrolled subjects.

**All Randomized Subjects:** All enrolled subjects who were randomized to a treatment arm (ipilimumab or DTIC). Unless otherwise indicated, analyses of most of study population and efficacy endpoints will be based on all randomized subjects and will be performed using the treatment group as randomized (i.e. on an intent-to-treat basis). Analyses of QoL will also be based on the all randomized subjects population: subjects with both baseline and on-study measurements will contribute to the analyses of change at on-study time-points.

**Response Evaluable Subjects:** All randomized subjects who have measurable disease (i.e., at least one measurable lesion) at baseline.

**All Treated Subjects:** All subjects who received at least one dose of treatment with ipilimumab or DTIC. Unless otherwise specified, analyses of safety and extent of exposure will be based on

all treated subjects. Analyses of all treated subjects will be performed using the treatment group as treated.

**Pharmacokinetic Subjects:** All available pharmacokinetic data from subjects who received ipilimumab will be included.

**ADA Evaluable Subjects:** All treated subjects with baseline and at least one post-baseline ipilimumab immunogenicity assessment

## 7 STATISTICAL ANALYSES

### 7.1 General Methods

No interim analyses are planned for this study. The final analysis will be performed when a minimum of 2 year follow-up is reached by all randomized subjects.

Unless otherwise noted, the bulleted titles in the following subsections describe tabulations of discrete variables, by the frequency and proportion of subjects falling into each category, grouped by treatment (with total). Percentages given in these tables will be rounded to the first decimal and, therefore, may not always sum to 100%. Percentages less than 0.1 will be indicated as ‘< 0.1’. Continuous variables will be summarized by treatment group (with total) using the mean, standard deviation, median, minimum and maximum values. Subject listings will be produced to accompany the tabulations. Time-to-event variables (e.g. time-to resolution) will be analyzed using the Kaplan-Meier technique. When specified, the median will be reported along with 80% CI using Brookmeyer and Crowley method (using log-log transformation for constructing the confidence intervals). The conventions to be used for imputing partial dates for analyses requiring dates are described in [Section 8](#).

Frequency tables of subject characteristics and subset analyses of efficacy endpoints (including those by M-substage and BRAF mutation status) will be based on the assessment recorded on the baseline CRF. However, stratified analyses will be based on the variables used by the IVRS to randomize the subject.

Assessments taken during re-induction and subsequent progression follow-up phase will not contribute to derived endpoints, such as BOR or PFS, since these assessments are necessarily following an initial progression. However exploratory version of these endpoints corresponding to the administration of re-induction therapy may be performed (if there are sufficient data) - details will be provided in the DPP.

All statistical analyses will be carried out using SAS software (SAS Institute, Cary, North Carolina, USA), unless otherwise noted.

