### **Immune-Related Adverse Events**

Summaries irAEs will be based on all treated subjects and will use the pre-defined list of MedDRA high-level group terms, high-level terms and preferred terms that is current at the time of analysis. ([APPENDIX 1](#) contains the most recent version of the list, version 20.0)

The following summary tables of irAEs will be restricted to events occurring in the on-study phase (see [Section 4.3.1.1](#)).

- On-study phase irAEs (worst CTC grade [Any grade, 3-4, 5] of any event and of events by SOC)
- On-study phase irAEs (worst CTC grade [1, 2, 3, 4, 5, unknown, any grade] of any event and of events by SOC)
- On-study phase irAEs by subcategory (worst CTC grade [Any grade, 3-4, 5] by subcategories of GI, liver, skin, endocrine, neurological, other)
- On-study phase irAEs by subcategory (worst CTC grade [1, 2, 3, 4, 5, unknown, any grade] by subcategories of GI, liver, skin, endocrine, neurological, other)
- Time to onset of on-study phase grade 3-5 irAEs by subcategory (GI, liver, skin, endocrine, neurological).
- Time to resolution of on-study phase grade 3-4 irAEs by subcategory (GI, liver, skin, endocrine, neurological)
- Number of episodes of on-study phase grade 3-4 irAEs by subcategory (GI, liver, skin, endocrine, neurological)

Listings by subject will be produced for all on-study and post-study irAEs (including steroid therapy received and details of resolution).

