### **Immune-Mediated Adverse Reactions**

Summaries of imARs will be based on all treated subjects.

The following summaries for on-study phase imARs will be provided (for subcategories as specified in the core imAR SAP):

- Summary of subjects with worst grade of grade 2 on-study phase imAR
- Summary of subjects with worst grade of grade 3-4 on-study phase imAR

- Summary of subjects with worst grade of grade 5 on-study phase imAR
- Summary of subjects with worst grade of grade 2-5 on-study phase imAR and outcome of hospitalization by subcategory (worst CTC grade [2+, 3-4, 5] by subcategories)
- Summary of subjects with worst grade of grade 2-5 on-study phase imAR who received blood transfusion by subcategory (worst CTC grade [2+, 3-4, 5] by subcategories)
- Time to first onset (any grade) of imARs for subjects with worst grade of grade 2-5 on-study phase imAR by subcategory
- Time to resolution of imARs for subjects with worst grade of grade 2-5 on-study phase imARs by outcome of resolution by subcategory
- Time to resolution of imARs for subjects with worst grade of grade 2-5 on-study phase imARs by use of systemic corticosteroids and outcome of resolution by subcategory
- Time to resolution of imARs for subjects with worst grade of grade 2-5 on-study phase imARs by use of high dose systemic corticosteroids and outcome of resolution by subcategory
- Time to resolution of imARs for subjects with worst grade of grade 2-5 on-study phase dermatitis imARs by use of topical corticosteroids and outcome of resolution
- imARs leading to study drug discontinuation by use of high dose systemic corticosteroids for subjects with worst grade of grade 2-5 imARs, by subcategory
- Distribution of outcome (last reported grade) of imARs for subjects with worst grade of grade 2-5 on-study phase imARs by subcategory
- Distribution of outcome (last reported grade) of imARs for subjects with worst grade of grade 2-5 on-study phase imARs by use of systemic corticosteroids by subcategory
- Distribution of outcome (last reported grade) of imARs for subjects with worst grade of grade 2-5 on-study phase imARs by use of high dose systemic corticosteroids by subcategory
- Distribution of outcome (last reported grade) of imARs for subjects with worst grade of grade 2-5 on-study phase dermatitis imARs by use of topical corticosteroids
- Distribution of outcome (last reported grade) of imARs for subjects with worst grade of grade 3-5 on-study phase imARs by subcategory

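### Time to resolution of irAEs and imARs is planned by Kaplan-Meier with no visible rule for death before resolution, and fatal irAEs drop out of the resolution table; both favour the drug

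*SAP*

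**What the plan says.** SAP Section 7.1 (General Methods) sets the method: "Time-to-event variables (e.g. time-to resolution) will be analyzed using the Kaplan-Meier technique". It adds: "When specified, the median will be reported along with 80% CI using Brookmeyer and Crowley method".

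SAP Section 7.6.1 then lists the tables to which this applies.

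- irAEs: "Time to resolution of on-study phase grade 3-4 irAEs by subcategory (GI, liver, skin, endocrine, neurological"). The line directly above it, on time to onset, covers grades 3-5.
- imARs: "Time to resolution of imARs for subjects with worst grade of grade 2-5 on-study phase imARs by outcome of resolution by subcategory". Further versions are split by corticosteroid use, and the endocrinopathy list has one of its own. These tables take worst grade 2-5, so fatal imARs are in them.
- imAR outcome, without Kaplan-Meier: "Distribution of outcome (last reported grade) of imARs for subjects with worst grade of grade 2-5 on-study phase imARs by subcategory".

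The imAR summaries are to be produced "for subcategories as specified in the core imAR SAP", a separate document. SAP Section 4.3.1.1, on AEs, irAEs and imARs, is in the table of contents, but its text was not available for this review.

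For other durations the SAP does say what death does. In Sections 4.2.3, 4.2.6 and 4.2.7, death counts as an event for PFS (unless subsequent therapy came first), duration of response and duration of stable disease. Section 8 gives imputation rules for dates of death, progression and last tumor assessment, but none for resolution.

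**The concern.** Kaplan-Meier assumes that a censored subject would have gone on to have the event at the same rate as those still followed. A subject who dies with an unresolved toxicity cannot resolve. If that death is coded as censoring, the curve estimates resolution in a setting where nobody dies, and its complement to one exceeds the share of toxicities that actually resolve. For a fatal imAR the effect is plainly wrong: a subject killed by the reaction is treated as someone in whom it might still have cleared.

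The irAE table has a different fault, which needs no inference about censoring. An irAE of grade 5 counts in the onset table and is absent from the resolution table, so the events that certainly did not resolve are taken out of that summary. Grade 3-4 irAEs can also be cut off by death from another cause, so the question of the death rule arises there too.

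At stake is how a reader of the study report judges the reversibility of immune toxicity with ipilimumab. The primary comparison is not involved.

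**Working it through.** **Inputs from the documents.** SAP Section 5 assumes exponential survival with a "12 month median OS for the ipilimumab arm with an 8 month median OS in the DTIC arm", "assuming a HR [ipilimumab vs DTIC] of 0.67". These agree with each other: 8/12 = 0.667; 2-year survival is 0.5^(24/12) = 25% and 0.5^(24/8) = 12.5%, as the SAP states. The documents give no figure for resolution to reproduce.

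**Input that is an assumption.** Time to resolution is taken as exponential with a median of 2 to 26 weeks, shown as a range. Death and resolution are independent, and there is no other censoring.

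**Formulas.** Let m be the median resolution time in months (weeks × 12/52), D = 12 the median OS, and t the time in months.

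- Death before resolution: m/(m + D)
- 1-KM with death censored: 1 − 0.5^(t/m)
- Cumulative incidence with death competing: D/(m + D) × [1 − 0.5^(t/m + t/D)]

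**Example, 4 weeks (m = 0.923), t = 6.** 1-KM = 1 − 0.5^6.5 = 98.9%. Cumulative incidence = 12/12.923 × (1 − 0.5^7) = 0.9286 × 0.9922 = 92.1%.

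**Example, 26 weeks (m = 6), median.** Set 12/18 × (1 − 0.5^(t/4)) = 0.5. Then 0.5^(t/4) = 0.25 and t = 8 months = 34.7 weeks, against 26 weeks by Kaplan-Meier.

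| Assumed median (weeks) | Die unresolved | 1-KM, 6 months | Cumulative incidence, 6 months | Excess (points) | Time to 50% resolved with death competing (weeks) |
|---|---|---|---|---|---|
| 2 | 3.7% | 100.0% | 96.3% | 3.7 | 2.0 |
| 4 | 7.1% | 98.9% | 92.1% | 6.8 | 4.1 |
| 8 | 13.3% | 89.5% | 80.2% | 9.3 | 8.6 |
| 12 | 18.8% | 77.7% | 68.5% | 9.3 | 13.4 |
| 26 | 33.3% | 50.0% | 43.1% | 6.9 | 34.7 |

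Excesses are taken before rounding. A simulation of 200,000 subjects per case agreed within 0.2 points and 0.2 weeks (34.5 weeks in the last row).

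**Fatal imARs.** Protocol Table 1.4.1-1 gives, for ipilimumab 3 mg/kg alone, 34 + 16 + 2 + 1 = 53 subjects at grades 2 to 5, of whom 1 (1.9%) was grade 5. With gp100 it gives 58 + 40 + 2 + 5 = 105, of whom 5 were grade 5. Together that is 6/158 = 3.8%. Adding 2% fatal imARs to the 4-week simulation (assumed death at a mean of 1 month) gives 98.8% against 90.3% at 6 months, an excess of 8.5 points.

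**irAE grades side by side.** Onset covers grades 3, 4 and 5; resolution covers grades 3 and 4. Removing events that cannot resolve can only raise the summarised resolution.

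**The case against.** The strongest reply is that censoring at death is inferred. Kaplan-Meier does not itself fix how death is coded: if the dead are kept in the risk set as unresolved to the end of follow-up and nothing else is censored, the estimate equals the cumulative incidence. The rule may be in Section 4.3.1.1, the core imAR SAP or the Data Presentation Plan, to which Section 8 defers further conventions. This stands. One may say that no rule is visible, not that the plan lacks one. Splitting the imAR tables by outcome of resolution does not supply it.

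Second, the SAP never names 1-KM as the share resolved. It asks for a median when specified, and the last-reported-grade tables show imAR outcome without Kaplan-Meier. This also stands, and it narrows the point. It does not close it, because those tables carry no timing and the median itself shifts when resolution is slow.

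Several stronger readings are tempting but not supported.

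- *Death before resolution is common.* The documents do not show this. It ranges from 3.7% to 33.3% in the table above, according to an assumed resolution time, and fatal events were about 2 to 4% of grade 2-5 imARs in the earlier trial.
- *The bias is well above 10 points.* With medians of 1.5, 3 and 6 months read at 12 months, the same formulas give 99.6, 93.8 and 75.0% against 88.7, 77.5 and 58.3%, or 11 to 17 points. The arithmetic is right, but the result rests on slower resolution and a later reading time, neither of which the SAP specifies.
- *Endocrinopathies are hit hardest.* No resolution times by class are given.
- *Fatal irAEs vanish from the report.* They do not. They appear in the grade 5 columns, the onset table, the by-subject listings and the death tables of Section 7.6.3.
- *Time to onset needs the same estimator.* The imAR onset table is limited to subjects who had the event, so death before onset cannot compete.

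**Conclusion.** The point holds in a limited form. The omission of fatal irAEs from the resolution table is on the face of SAP Section 7.6.1. The Kaplan-Meier point is conditional: if death is censored, resolution is overstated, and fatal imARs are treated as still able to resolve. The direction is then certain under the model used.

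The size is not fixed by the documents. With the SAP's 12-month median OS and assumed resolution medians of 2 to 12 weeks, the excess at 6 months is about 4 to 9 points. The effect on the median is negligible for fast events and material for slow ones (26 to about 34.5 weeks). The figures assume exponential, independent times; subjects with unresolved toxicity may have a different death rate. This is a descriptive safety output, and neither the primary test nor its power is affected.

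**What to change.** In SAP Sections 7.1 and 7.6.1:

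1. State how death before resolution is handled, including grade 5 imARs. If Section 4.3.1.1 or the core imAR SAP already does so, cite it.
2. Report the cumulative incidence of resolution (Aalen-Johansen) with death as a competing event, for irAEs and imARs.
3. Widen the irAE resolution table from grade 3-4 to grade 3-5, with fatal events counted as unresolved.

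The cost is a little extra programming and slightly less favourable resolution figures. No new data are needed, since death dates are already collected and tabulated. The Protocol gives a database lock of 03 June 2019, so in practice this means added or corrected tables in the study report, labelled as such.
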